#### 8.7. Allocation of Intervention

Eligible participants will be randomised 1:1 to one of the two arms using a web-based randomisation portal using blocks of randomly varying length.

An immediate allocation of treatment intervention as well as a participant identification number will be provided by the system to the person entering the data.

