#### 13. STATISTICS AND ANALYSIS

### 13.1 Description of Statistical Methods

The two arms (Favipiravir vs Standard of Care) will be compared with time-to-event analysis using a competing-risks survival regression based on Fine and Gray's proportional subhazards model. All analysis will be performed on an intention to treat basis.

Patient improvement will be monitored for 28 days or until death. It is not expected that any patient will be lost to follow-up, even if discharged home. Kaplan-Meier plots will be constructed showing the probability of survival in each treatment group. Schoenfeld Residuals will be plotted and tested over time to examine the assumption of proportional hazards; with a restricted mean survival time analysis (RMST) as an alternative method for analysis for the proportional hazards assumption is not met.

Similarly, patients who discontinued the clinical trial or administration of the study drug due to worsening of symptoms/lack of efficacy (including patients who switched to rescue therapy) but remain alive will be handled as cases right-censored as of day 28, with no clinical improvement.

Additional secondary analysis of the primary outcome will be undertaken that adjust for, or involves a sub-set of patients, and examines the effect of

- (a) country of recruitment
- (b) time from onset of symptoms (median split)
- (c) limited to those patients with confirmed SARS-COV-2 infection
- (d) by high or low (median split) viral load.
- (e) early or late during recruitment to the study to examine improves in clinical care and understanding.

Other secondary analysis have been pre-specified in the statistical analysis plan and listed on clinical trials.gov. Differences between the two trial arms will be compared by standard and appropriate statistical tests.

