#### Primary outcome measure

The primary end-point of this study is the time from randomisation to a sustained clinical improvement (maintained for 24 hours) by two points on a seven-category ordinal scale or to discharge, whichever happens first (recommended by WHO)(10).

The seven-category ordinal scale (23):

- 1: Not hospitalised with resumption of normal activities
- 2: Not hospitalised, but unable to resume normal
- 3: Hospitalised, not requiring supplemental oxygen
- 4: Hospitalised, requiring supplemental oxygen
- 5: Hospitalised, requiring nasal high-flow oxygen therapy, non-invasive mechanical ventilation or both
- 6: Hospitalised, requiring ECMO (Extra-corporal membrane oxygenation), invasive mechanical ventilation or both
- 7: Death

This study will recruit 500 participants in total. We have chosen a primary outcome measure, previously used in influenza trials, of a 2-point change in a scale of clinical status (13, 14). No simpler continuous measure was considered appropriate due to the heterogeneous clinical presentation of COVID-19 infection at hospital admission. In a trial investigating influenza, significant difference in time to a 2 point improvement on the 7-point scale scoring system has been found, with a difference between groups of 40 patients on combined Favipiravir and Oseltamivir, compared with 128 patients on Oseltamivir only (p=0.0477)(10). PIONEER will have 250 patients in each group and will thus we will be able to detect similar improvements seen with these anti-viral agents (appreciably used in the treatment of influenza infection), at an alpha of 0.05

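### Country of recruitment enters only a secondary analysis; stratifying the primary Fine-Gray model by country would cost almost nothing and would protect power if discharge timing differs between countries

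*Protocol*

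**What the plan says.** Protocol Section 13.1 states that the two arms will be compared by Fine and Gray's subhazards regression, by intention to treat. It mentions no covariate and no stratum for that comparison. It then says: "Additional secondary analysis of the primary outcome will be undertaken that adjust for, or involves a sub-set of patients, and examines the effect of", followed by five items, of which the first is "a) country of recruitment".

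Section 8.7 describes the allocation: "Eligible participants will be randomised 1:1 to one of the two arms using a web-based randomisation portal using blocks of randomly varying length". No stratification factor is named.

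The primary event (Sections 6.4 and 13.2) is a two-point improvement on the seven-category scale, sustained for 24 hours, "or to discharge, whichever happens first".

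On size, Section 13.2 says "This study will recruit 500 participants in total" and "PIONEER will have 250 patients in each group", with a test "at an alpha of 0.05". It gives no power, target hazard ratio or expected number of events. Recruitment is global (Section 8.1), and UK and Belgian sites are mentioned (Sections 7.1 and 15.8). The number of countries and their shares are not given.

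**The concern.** The protocol recognises country as worth examining for the primary outcome but gives it a secondary role, so the stated design uses it neither at randomisation nor in the confirmatory test.

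The endpoint makes this worth attention. From category 4, two points better is category 2, which is already out of hospital. From category 3, discharge also comes first. From categories 5 and 6 the event can occur in hospital (5 to 3, 6 to 4). For patients entering at 3 or 4, the time to event is therefore the time to discharge, which may depend on local practice as well as on recovery.

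In a proportional (sub)hazards model, leaving out a prognostic factor moves the estimated ratio towards 1 and lowers power, even when the arms are balanced on that factor. Country is presumably known for every patient, so what is at stake is power that could be protected without collecting anything new. There is also an interpretive cost: if the country-adjusted and primary results fell on opposite sides of 0.05, the analysis that uses the known design feature would be the secondary one.

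**Working it through.** **1. The plan's own figure.** The 500 cannot be reproduced, because no target ratio, event share or power is stated. The only anchor is the cited influenza comparison, 40 v 128 patients, p = 0.0477 (z = 1.980). With a = 40/168 = 0.238 and d events, log HR = z / √(d·a·(1−a)).
- All 168 with an event: 1.980/√(168 × 0.1814) = 0.359, HR 1.43.
- Half with an event (d = 84): 1.980/√(84 × 0.1814) = 0.507, HR 1.66.

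By Schoenfeld's formula (two-sided 0.05, 1:1), 80% power needs log HR = (1.960 + 0.842)/√(500·g/4), where g is the event share. For g = 0.90 this gives HR 1.30 and for g = 0.60 HR 1.38. The event shares are assumptions.

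**2. Set-up of the simulations.** With complete follow-up to day 28, the Fine-Gray test of arm amounts to a log-rank test in which patients who die stay in the risk set to day 28. Unstratified: U = Σ(x − p) and V = Σp(1−p) over events, where x is 1 for favipiravir and 0 for control and p is the favipiravir share of those at risk; z = U/√V. Stratified: U and V are computed within each country and summed before taking z. Each setting has 4,000 trials, N = 500, 1:1, rejecting at |z| > 1.96.

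**3. Two countries.** Assumed: median 9 days, constant subhazards, no separate group of deaths (84 to 92% with events by day 28).

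| True HR | Country split | Country HR | Unstratified % | Stratified % | Difference |
|---|---|---|---|---|---|
| 1.30 | equal | 1.0 | 79.8 | 79.7 | −0.1 |
| 1.30 | equal | 1.5 | 77.1 | 79.2 | 2.1 |
| 1.30 | equal | 2 | 72.2 | 79.1 | 6.9 |
| 1.30 | equal | 3 | 61.1 | 78.1 | 17.0 |
| 1.30 | 80/20 | 1.5 | 78.1 | 79.3 | 1.2 |
| 1.30 | 80/20 | 2 | 75.6 | 79.3 | 3.7 |
| 1.30 | 80/20 | 3 | 71.0 | 78.6 | 7.6 |
| 1.43 | equal | 1.5 | 95.8 | 96.8 | 1.0 |
| 1.43 | equal | 2 | 93.4 | 96.1 | 2.7 |
| 1.43 | equal | 3 | 87.2 | 95.8 | 8.6 |

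At true HR 1.30 with equal countries, the unstratified log HR estimate is 0.266 with no country effect and shrinks to 0.258, 0.244 and 0.218 at country HR 1.5, 2 and 3. The stratified estimate stays at 0.266 to 0.267. Under no treatment effect, the rejection rate is 4.9 to 5.4% unstratified and 4.3 to 5.5% stratified.

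**4. Five countries.** Assumed: control median 9 days, 10% deaths kept at risk as never improving, effect set for about 80% power without country variation, country log-hazards varying with the SD shown.

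| SD | Unstratified % | Stratified % | Difference |
|---|---|---|---|
| 0 | 80 | 79 | −1 |
| 0.3 | 75 | 77 | 2 |
| 0.5 | 69 | 74 | 5 |
| 0.7 | 64 | 74 | 10 |

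A separate five-country run gave gains of about 1, 4 and 7 to 9 points at SD 0.3, 0.5 and 0.7, and about 0 with no country variation. Compare the two columns within a row: part of the fall down the table is not recovered by stratifying. Patients who never improve dilute the contrast between countries, so the two-country losses, which have no such group, lie on the high side.

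**5. Scale of the assumptions.** Between countries at +1 and −1 SD, the improvement rates differ by exp(2 × 0.3) = 1.8-fold, exp(2 × 0.5) = 2.7-fold and exp(2 × 0.7) = 4.1-fold.

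**The case against.** The strongest reply is that nothing is invalid. The unstratified test holds its type I error, matches a randomisation that names no strata, and estimates a marginal subhazard ratio, which is a legitimate target. The shift towards 1 is the difference between a marginal and a within-country ratio, not bias. All of that stands: this is an efficiency point.

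It can also be said that strata are commonly left to the SAP, which is not at hand, and that Section 13.1 never uses the word unadjusted. But the section does more than stay silent, because it assigns country to a secondary analysis. An SAP that put country in the primary model would sit awkwardly with that. The list does not say which items are adjustments and which are subsets, so it should not be read as a commitment to adjust for country.

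Three stronger readings may tempt a reader, and the protocol supports none of them.
- That the event is mostly discharge. This depends on how many patients enter in categories 3 and 4, and no baseline mix is given.
- That discharge timing depends on national practice. This is plausible, but no section says so or gives a figure.
- That the unstratified test loses power for no benefit. Any loss is conditional on country differences, and the test keeps a marginal interpretation and up to about 1 point of power if countries are alike.

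Timing is a fair objection too. This is version 2.4 of April 2021. Enrolment began in May 2020, the study ends in October 2021, and Section 13.3 plans an interim analysis from 90 patients. Changing a confirmatory model late in an open-label trial can look data-driven. That does not defeat the proposal, but it governs when and by whom it may be made.

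**Conclusion.** The point holds as a cheap improvement, not as an error of validity. Section 13.1 states the primary comparison without a stratum and confines country to a secondary analysis, and Section 8.7 names no stratified randomisation.

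At a design with about 80% power, the loss is 1 to 2 points for modest country differences (ratio 1.5 or SD 0.3) and about 3 to 7 points for a ratio of 2 or SD 0.5. Losses of roughly 7 to 17 points need extreme differences (ratio 3 or SD 0.7). If the true effect is as large as the cited study implies (HR 1.43 or more), the loss is about 1 point at a country ratio of 1.5 and under 3 at a ratio of 2. If countries do not differ, there is no loss.

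The size rests entirely on assumed country differences, numbers and shares of countries, and event rates. The direction and the near-zero cost of stratifying do not depend on which of these values is chosen.

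**What to change.** In Section 13.1, and in the SAP to match:
- Stratify the primary Fine-Gray model by country, with a separate baseline subhazard for each, and pool small countries by a rule fixed in advance.
- Report the unstratified model as a sensitivity analysis.
- Keep item (a) of the secondary list for treatment-by-country heterogeneity.
- Make and document the change before database lock and before anyone choosing the model has seen comparative data. Section 16.1 already keeps interim results from the Chief Investigator and study staff unless the DSMB finds decisive evidence on mortality; the record should confirm that this held for those making the change.
- Check that the weighted log-rank or Cox statistic in Section 13.3 and the RMST fallback in Section 13.1 treat country in the same way.

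The cost is a wording amendment, 0 to 1 point of power if countries do not differ, and a primary estimate that is a within-country rather than a marginal subhazard ratio, which the report should say.

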## 6.3. Exploratory Objectives

• To identify prognostic markers indicating the need for early intervention with Favipiravir in patients with COVID-19 infection

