#### **Exploratory Objectives**

To identify prognostic markers indicating the need for early intervention with Favipiravir in patients with COVID-19 infection.

To assess the pharmacokinetics and pharmacodynamics of Favipiravir

- Change in viral PCR titres at post-randomisation time points relative to baseline
- Change in host transcriptome profiles at post randomisation time points relative to baseline
- Computer tomography quantitative analysis
- Favipiravir pharmacokinetics and pharmacodynamics properties at day 5 to 10.

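### Median splits of time from symptom onset and viral load in the secondary analyses discard information about whether the treatment effect varies with them

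*Protocol*

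**What the plan says.** Protocol section 13.1 sets the primary comparison as a Fine-Gray competing-risks regression. It then adds: "Additional secondary analysis of the primary outcome will be undertaken that adjust for, or involves a sub-set of patients". Five items follow. Item (b) is "time from onset of symptoms (median split" and item (d) is "by high or low (median split) viral load". Only further secondary analyses, beyond these five, are referred to the statistical analysis plan, so the two median splits are fixed in the protocol itself.

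The data behind both variables are finer than two groups. Section 10.1 collects the date of symptom onset. Section 6.4 lists as an exploratory endpoint: "Change in viral PCR titres at post-randomisation time points relative to baseline". Section 10.4 schedules a nasopharyngeal swab at baseline, between days 5 and 10, and between days 14 and 28. It also says that not every exploratory research sample is needed from every participant, with sampling agreed site by site. Item (d) does not say which swab defines viral load.

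**The concern.** A median split treats a patient just above the median like the one furthest above it, and unlike the one just below it. The cut is the median of whoever enrols, so it is known only after recruitment and carries no stated clinical meaning. The trial studies early treatment, and the entry criteria in sections 8.2 and 8.3 set no limit on symptom duration. How the effect varies with time from onset is therefore a natural secondary question, and this analysis should use the data fully.

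The two routes named, adjusting for a factor or analysing a subset, do not by themselves estimate a difference in treatment effect. Adjustment gives the factor's own association with outcome, and two separate halves give two estimates without a comparison. At stake is precision on effect modification, and a result stated for two arbitrary halves where it could be given across the range of the modifier.

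**Working it through.** **Inputs from the protocol.** 500 participants, 250 per arm, alpha 0.05 (section 13.2); 1:1 allocation (section 8.7); 28 days of follow-up (section 13.1).

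**Assumptions.** Two-sided test (the protocol does not say), complete data, linear effect modification, normal modifier unless noted, 350 to 450 improvement events.

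**The plan's own figure.** There is none to reproduce here: the protocol gives no power, hazard ratio or event count for these analyses, or for the choice of 500. As a check on the main comparison, the influenza study in section 13.2 has 40 against 128 patients and p = 0.0477, so z = 1.98. Scaling gives 1.98 × sqrt[(250×250/500)/(40×128/168)] = 1.98 × sqrt(125/30.48) = 4.01, and Phi(4.01 − 1.96) = 98%, if that observed effect were true and the event fraction the same. This says nothing about effect modification.

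**Information kept.** The relative efficiency of the split is the squared correlation between the binary split and the correctly scaled modifier. For a normal modifier it is 2/pi = 0.637.
- 500 × 0.637 = 318, so 500 patients inform the interaction as about 318 would with continuous data.
- 500 / 0.637 = 785 would be needed with a split to match 500 with continuous data.

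**Power.** Split power = Phi[(1.96 + z_power) × sqrt(efficiency) − 1.96].
- From 80%: Phi(2.802 × 0.798 − 1.96) = Phi(0.28) = 61%.
- From 90%: Phi(3.242 × 0.798 − 1.96) = Phi(0.63) = 73%.

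**Other distributions of the modifier.**

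| Modifier | Efficiency of split | 80% becomes |
|---|---|---|
| Uniform | 0.75 | 68% |
| Normal | 0.64 | 61% |
| Exponential | 0.48 | 49% |
| Lognormal, log-SD 0.4 to 0.8 | 0.56 to 0.37 | not tabulated |

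For the lowest value, Phi(2.802 × sqrt(0.37) − 1.96) = Phi(−0.26) = about 40%.

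**In hazard-ratio terms.** Power = Phi[sqrt(events/4 × efficiency) × ln(ratio of HRs per SD) − 1.96]. With 400 events and a ratio of 1.3 per SD:
- continuous: Phi(10 × 0.262 − 1.96) = 75%
- split: Phi(10 × 0.798 × 0.262 − 1.96) = 55%

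Over 350 to 450 events the ranges are 69 to 80% and 50 to 60%. Even with a formal interaction test, a split at 400 events needs hazard ratios in the two halves to differ by exp(2.802/sqrt(400/16)) = 1.75-fold for 80% power.

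**Simulation.** Cox model, 400 trials per setting, n = 500, censoring at 28 days, no competing deaths, about 443 events.

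| Ratio of HRs per SD | Continuous | Split |
|---|---|---|
| 1.0 | 5.3% | 7.0% |
| 1.2 | 48% | 31% |
| 1.3 | 78.5% | 56% |

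The rejection rates with no interaction differ from 5% by no more than simulation noise. The Cox model stands in for Fine-Gray; the relative loss should be similar.

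**Where the continuous term does worse.** If the effect is a step exactly at the median, the linear term keeps only 0.64. If the effect is linear in the log of the modifier and the raw scale is used, the linear term keeps 0.92 to 0.71 for log-SD 0.4 to 0.8. The split keeps 0.64 there, because it does not depend on the scale.

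**The case against.** A median split fixed in advance prevents choosing a cut-point from the results, is easy to report, and can place undetectable viral loads in the low group without further rules. The size of the loss depends on the modifier's distribution and on the shape of the interaction, and the trial claims no interaction power. Even the continuous test has only 48% power in the simulation at a ratio of 1.2 per SD. Baseline viral load will be missing for some participants, and patients admitted on suspicion may have no detectable virus. All of this stands and limits the point. It does not rescue the split as the main analysis, because a continuous interaction specified in advance is equally protected from cut-point selection.

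A reader might infer several stronger things that the protocol does not support:
- **That no interaction will be tested, or that one significant half will be read as a subgroup effect.** The analysis plan is not shown and could add an interaction test. The fixed median split is what the protocol settles.
- **That the marker objective is served only by post-randomisation changes.** Section 6.4 lists its exploratory endpoints jointly for the marker objective and the pharmacokinetic and pharmacodynamic objective. Quantitative CT analysis, for one, is not described as a change.
- **That the main aim is to find who benefits.** The primary objective is the overall treatment effect. The aim "To identify prognostic markers indicating the need for early intervention with Favipiravir in patients with COVID-19 infection" is exploratory.
- **That every listed item should become an interaction.** Item (c) restricts the population to confirmed infection, which is a different question.

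**Conclusion.** The point holds for items (b) and (d). Under a normal modifier and a linear interaction, the median split keeps about 64% of the information and turns 80% interaction power into about 61%. Retained efficiency is about 0.37 to 0.75 across the other distributions tried, and a step exactly at the median reverses the comparison. These figures assume complete data, so absolute power for viral load would be lower under either method. The 80% starting value is a benchmark and not a claim of the trial. The primary comparison is unaffected, so this is an improvement to secondary analyses and not a threat to the main result.

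**What to change.** Replace (b) and (d) in section 13.1, and carry the change into the analysis plan, with text such as: *Effect modification by days from symptom onset and by baseline log viral load will each be examined by a treatment-by-modifier interaction in the Fine-Gray model, with the modifier continuous (linear, with a spline as check). The interaction estimate with its confidence interval and the treatment effect across the range of the modifier will be reported. Any median split is a descriptive display.*

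For viral load, also state that the baseline sample is used, since later swabs follow randomisation and may reflect treatment. Give a rule for undetectable values, and report by arm how many participants have a baseline value.

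The cost is wording only, with no new data: onset date is already collected and a baseline swab is already scheduled, though not assured for everyone. The small downside is that a functional form and a non-detect rule must be fixed in advance.

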#### 13.2 Sample Size Justification

## **Primary Objective**

To determine whether early intervention with Favipiravir improves the time to significant improvement in clinical status in patients with COVID-19 infection

#### Primary outcome measure

The primary end-point of this study is the time from randomisation to a sustained clinical improvement (maintained for 24 hours) by two points on a seven-category ordinal scale or to discharge, whichever happens first (recommended by WHO)(10).

The seven-category ordinal scale (23):

- 1: Not hospitalised with resumption of normal activities
- 2: Not hospitalised, but unable to resume normal
- 3: Hospitalised, not requiring supplemental oxygen
- 4: Hospitalised, requiring supplemental oxygen
- 5: Hospitalised, requiring nasal high-flow oxygen therapy, non-invasive mechanical ventilation or both
- 6: Hospitalised, requiring ECMO (Extra-corporal membrane oxygenation), invasive mechanical ventilation or both
- 7: Death

This study will recruit 500 participants in total. We have chosen a primary outcome measure, previously used in influenza trials, of a 2-point change in a scale of clinical status (13, 14). No simpler continuous measure was considered appropriate due to the heterogeneous clinical presentation of COVID-19 infection at hospital admission. In a trial investigating influenza, significant difference in time to a 2 point improvement on the 7-point scale scoring system has been found, with a difference between groups of 40 patients on combined Favipiravir and Oseltamivir, compared with 128 patients on Oseltamivir only (p=0.0477)(10). PIONEER will have 250 patients in each group and will thus we will be able to detect similar improvements seen with these anti-viral agents (appreciably used in the treatment of influenza infection), at an alpha of 0.05

